7.0 Data and Specimen Banking*

N/A

8.0 Sharing of Results with Subjects*

8.1 Results will not be shared

9.0 Study Timelines*

- An individual study subject's participation in the study should last approximately 15-30 minutes total.
- All study subjects should be enrolled within 1 year of study start.
- The study should be completed within 2 years of study start.

10.0 Inclusion and Exclusion Criteria*

10.1 Potential subjects will be identified by reviewing the surgery schedule in Epic and will be recruited from the Surgery Unit pre-op area prior to their surgery.

10.2 Inclusion criteria: Age 0-21 years, requiring SLV for thoracic surgery.

Exclusion criteria: None.

10.3 We are including children, and will not include:

- Adults unable to consent
- Pregnant women
- Prisoners

11.0 Vulnerable Populations*

11.1 This study presents no more than minimal risk as it only involves ultrasound which is non-invasive, will add less than 10 minutes to the total anesthetic time, and written consent is normally not required.

12.0 Local Number of Subjects

12.1 80

12.2 Power calculation for this study was based on a previous study reporting the accuracy of ultrasonography (compared to FOB) for confirming lung isolation when using DLTs.¹¹ This study found the accuracy to be 84%-89% depending on which lung was isolated. Assuming that ultrasonography has an overall accuracy of 85%, a two-tailed, one-sample test of proportions would have >80% power to detect a difference of at least 10% when 80 patients are enrolled.

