2.0 Objectives

- 2.1 The primary objective is to determine the accuracy of auscultation and ultrasonography for confirming lung isolation during SLV, as compared to direct visualization using FOB (gold standard). The secondary objective is to compare the time required to confirm lung isolation using the above-mentioned techniques including auscultation, FOB, and ultrasound.
- 2.2 The hypothesis is that ultrasonography will have at least 80% accuracy for verifying lung separation during SLV as confirmed by FOB; and will have greater accuracy than auscultation.

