6.0 Procedures Involved*

PROTOCOL TITLE: Ultrasound to verify lung-isolation during single-lung ventilation

6.1 The proposed study will be conducted in 80 patients, ranging in age from 0 to 21 years. There will be no change in clinical practice regarding choice of anesthetic technique including premedication, device used for SLV, monitoring, induction, and maintenance of anesthesia. An investigator will identify patients in whom SLV is required for thoracic surgery. There will be total of three anesthesia providers and one surgeon involved in the study. One will be the primary anesthesiologist, who is one of the attending faculty and will be responsible for patient care during the perioperative period. They will decide prior to and during the case whether the patient is appropriate for and able to complete the study protocol. The other two anesthesia providers will be members of the study team or other anesthesia attending/fellow and will include an auscultator (may be a resident/CRNA/SRNA), the anesthesia provider who will perform the auscultation examination and the ultrasonographer, the anesthesia provider who will perform the ultrasound examination (see below). The surgeon will be the attending surgeon and will confirm the efficacy of one-lung ventilation during the surgical procedure. Both the auscultator and ultrasonographer will be blinded to the lung that is isolated.

The technique of SLV will be determined by the attending anesthesiology to include a DLT, bronchial blocker or main stem intubation with an ETT. The ventilator settings will be standardized until all of the study measurements and data have been collected:

Ventilation Mode: PRVC

RR titrated to achieve normocapnia

Inspiratory time 1 second

TV set at 6-8 ml/kg

PEEP: minimum of 5 cm H20

100% FiO2

6.2 After anesthetic induction the following ventilatory parameters will be recorded: tidal volume, peak inflating pressure, inspiratory time, respiratory rate, inspired oxygen concentration, end-tidal carbon dioxide, and oxygen saturation. After placement of the device for SLV, and isolation of the lung, the non-operative lung will be ventilated and the ventilatory parameters will be recorded again. Clinical confirmation of effective lung separation will include auscultation with documentation of absence of breath sounds on the operative side. Following this, correct placement of the DLT will be confirmed using FOB. The time to perform FOB will be determined.

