17.0 Data Management* and Confidentiality

17.1 We will compare the accuracy, sensitivity, and specificity of ultrasonography and auscultation (using FOB confirmation of one-lung isolation as the reference standard) using paired tests of proportions. As a secondary, exploratory aim, we will compare the time to perform each of the techniques using paired t-tests or sign-rank tests (according to the normality of the outcome distribution).

17.2 Research records will be stored in a locked cabinet and password protected computer. Only certified research personnel will be given access to identifiable subject information

17.3 Following publication of study results, research records will be stored for a period of 3-5 years and then will be destroyed by placing in a secure shredding bin.

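### The >80% power in section 12.2 has no stated comparator, direction or alpha, and on no reading checked is it the power of either part of the hypothesis in section 2.2

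*Combined protocol and SAP*

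**What the plan says.** Section 2.1 sets an estimation aim: "The primary objective is to determine the accuracy of auscultation and ultrasonography for confirming lung isolation during SLV", with bronchoscopy as the reference. Section 2.2 adds a two-part hypothesis: "ultrasonography will have at least 80% accuracy for verifying lung separation during SLV as confirmed by FOB; and will have greater accuracy than auscultation".

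The sample size is justified only in section 12.2. It cites an earlier study of double-lumen tubes ("This study found the accuracy to be 84%-89% depending on which lung was isolated"), continues "Assuming that ultrasonography has an overall accuracy of 85" percent, and concludes that a "two-tailed, one-sample test of proportions would have >80% power to detect a difference of at least 10" percent with 80 patients. It gives no reference proportion, no direction for the 10% and no alpha. Alpha is not given elsewhere either.

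Section 17.1 is the analysis plan. It compares the accuracy, sensitivity and specificity of ultrasound and auscultation "using paired tests of proportions". It lists no one-sample test, no comparison with 80% and no confidence interval.

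**The concern.** A one-sample test needs a fixed value to test against. With 85% assumed and a 10% difference, that value could be 75% or 95%, and either could be the null. A reader who has just met the 80% threshold in section 2.2 may take the >80% as the power to support that hypothesis, or the claim of superiority over auscultation. If it is neither, the only reason given for 80 patients is detached from what the study sets out to show.

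A second gap follows. Nothing says how the 80% threshold will be judged. If the point estimate alone decides, 64 of 80 correct would count as support. That result or better has probability 92% at a true accuracy of 85%, but also 18% at a true accuracy of 75% (an illustrative value).

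**Working it through.** **Inputs.** From section 12.2: n = 80, accuracy 85%, difference 10% (taken as percentage points), two-tailed one-sample test. From section 2.2: the 80% threshold. Assumed, because not stated: two-sided alpha 0.05 (z = 1.96) and one binary result per patient.

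**Formula (score, normal approximation).** Power = Φ[(|p1 − p0| − z·s0)/s1], where p0 is the null, p1 the true value, s0 = √(p0(1−p0)/n) and s1 = √(p1(1−p1)/n). At n = 80, s = 0.0484 at 75%, 0.0399 at 85% and 0.0244 at 95%. N for 80% power = [(1.96√(p0(1−p0)) + 0.8416√(p1(1−p1)))/(p1−p0)]², rounded up. The exact column uses the equal-tailed binomial test.

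**Reproducing the plan's figure.** With null 85% and true 95%: (0.10 − 1.96×0.0399)/0.0244 = 0.893, and Φ(0.893) = 81.4%. The required N is 78.02, so 79, close to the planned 80.

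| Null | True | Score power | Exact power | N for 80% (score) |
|---|---|---|---|---|
| 85% | 95% | 81.4% | 78.9% | 79 |
| 95% | 85% | 90.5% | 86.6% | 53 |
| 75% | 85% | 55.1% | 57.6% | 133 |
| 85% | 75% | 67.3% | 54.3% | 114 |

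In the last row a minimum-likelihood exact test gives 64%, so the exact span against 75% is 54% to 64%.

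**Sensitivity to the unstated choices.**
- Single-SE formula with the variance at 85%, against 75%: Φ(0.10/0.0399 − 1.96) = 71%. At two-sided alpha 0.10 it is Φ(0.10/0.0399 − 1.645) = 80.5%. Score and exact powers at alpha 0.10 are 69.5% / 69.1% (null 75%) and 76.1% / 73.6% (null 85%).
- 10% read as relative (85% against 93.5%): a single-SE formula with the variance at 93.5% gives 86.9% at alpha 0.05. The score formula with 93.5% as null gives 78.1% at alpha 0.05 and 84.0% at alpha 0.10.
- 160 lung fields counted as independent, against 75%: about 88% to 90%.

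**Does any of these test the hypothesis?** The null or alternative is 75%, 95%, 93.5% or 85% itself. None is the 80% of section 2.2, none involves auscultation, and the one-sample test is not in section 17.1.

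**The paired comparison.** With difference d and discordance ψ, normal-approximation McNemar power is Φ[(d√n − 1.96√ψ)/√(ψ − d²)]. The plan gives no auscultation accuracy, so both values below are assumptions.
- Auscultation 75% (d = 0.10): 82% at the minimum discordance of 10%; 35% if errors are independent (ψ = 0.85×0.25 + 0.15×0.75 = 0.325).
- Auscultation 65% (d = 0.20): 83% (exact 79%) if errors are independent (ψ = 0.85×0.35 + 0.15×0.65 = 0.395).

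**Precision.** Exact (Clopper-Pearson) 95% intervals: 64/80 = 80%, 69.6% to 88.1%; 68/80 = 85%, 75.3% to 92.0%.

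**The case against.** The strongest reply is that section 12.2 contains no error. With 85% as null, 95% as alternative and two-sided 0.05, the standard formula gives 81.4% and N = 79, which matches the plan. That stands: the sentence is under-specified but can be reproduced. One qualification is that the exact test with 85% as null gives 78.9%, so in that direction the match depends on the approximation.

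A reader might infer that 95% must be the value the sponsor used. The documents do not support this. Alpha, formula and unit are all unstated, and some combinations pass 80% against 75% or for a relative 10%. Section 4.1 describes accuracy in terms of both lungs, so the unit is not beyond question, although section 12.2 counts patients.

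A reader might also infer that the study is underpowered. A score test of 80% as null at a true 85% would have power Φ[(0.05 − 1.96×0.0447)/0.0399] = 17% (exact 13%). The plan proposes no such test, and its primary objective is to estimate accuracy. Nor is the auscultation comparison shown to be underpowered: the result depends on inputs the plan does not give.

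Finally, section 12.2 does not itself say that its power belongs to section 2.2, no decision rule depends on it, and the remedy is text only. That argues for lower severity. It does not remove the point, because writing 95% and alpha into section 12.2 would still leave the sample size resting on an unplanned test unrelated to the hypothesis.

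**Conclusion.** The point holds as a mismatch between the stated power, the hypothesis and the analysis. At two-sided alpha 0.05, one result per patient and the score formula (all assumed), >80% fits 85% against 95%, a value above the cited 84% to 89% range and found nowhere in the plan. It does not fit 75%: 55% to 67% by score, 54% to 64% exact, at most 71% by the single-SE formula. The conclusion does not depend on which reading the sponsor used, since none of those checked addresses the 80% threshold or superiority over auscultation, and none is a planned analysis. It should be fixed, but it does not undermine the design or the choice of 80 patients.

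**What to change.** Keep 80 patients and make three text changes.

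1. **Section 12.2.** Either state the null, the alternative and alpha, and say that the resulting power addresses neither part of section 2.2; or replace the power sentence with expected precision, which suits the primary objective: if 68 of 80 patients are classified correctly (85%), the exact 95% CI is 75% to 92%.
2. **Section 17.1.** Add ultrasound accuracy with an exact 95% CI and name the unit of analysis; per patient matches the 80 in section 12.2. Judge the 80% threshold with that interval shown, not from the point estimate alone: 64/80 meets 80% but has an interval of 70% to 88%.
3. **Comparison with auscultation.** Say that it has no stated power because no auscultation accuracy or discordance is assumed.

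The cost is wording only, with no extra patients and no change to data collection. The sponsor gives up a favourable-looking power figure, or qualifies it, and must say how the 80% threshold will be judged.

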13.0 Recruitment Methods

13.1 Subjects will be recruited from the surgery unit pre-op area. They will be identified by reviewing OR schedules in Epic.

14.0 Withdrawal of Subjects*

N/A

15.0 Risks to Subjects*

15.1 Although not likely, there may be a potential risk for breach of patient health information. There are no study related physical risks to study subjects associated with this study. All study related procedures are non-invasive.

15.2 Subject information will not be given to any other investigators. Subjects and their information will be closely monitored and guarded by study staff; there will be limited access to patients and their information by trained study staff; and subject information will only be shared and discussed between study staff specific to this study. Subject PHI will be stored in a locked cabinet, and will be stored and maintained in password protected computer files.

16.0 Potential Benefits to Subjects*

16.1 No direct benefit to the subject.

17.0 Data Management* and Confidentiality

17.1 We will compare the accuracy, sensitivity, and specificity of ultrasonography and auscultation (using FOB confirmation of one-lung isolation as the reference standard) using paired tests of proportions. As a secondary, exploratory aim, we will compare the time to perform each of the techniques using paired t-tests or sign-rank tests (according to the normality of the outcome distribution).

17.2 Research records will be stored in a locked cabinet and password protected computer. Only certified research personnel will be given access to identifiable subject information

17.3 Following publication of study results, research records will be stored for a period of 3-5 years and then will be destroyed by placing in a secure shredding bin.

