3.0 Background

- 3.1 During thoracic surgery, specific anesthetic techniques are used to isolate the lungs and allow for single-lung ventilation (SLV) so that the ipsilateral lung is not ventilated during the surgical procedure.¹⁻³ A motionless lung on the side of surgery is necessary to allow for the surgical procedure to proceed optimally. To accomplish SLV, there are several options including use of a specialized double-lumen

PROTOCOL TITLE: Ultrasound to verify lung-isolation during single-lung ventilation

endotracheal tube (DLT), placement of a bronchial blocker into the main stem bronchus of the operative side, or selective main stem intubation with a standard endotracheal tube (ETT). All of these devices allow for selective ventilation of the non-operative lung. In common clinical practice, the placement of the device for SLV may be guided by direct vision using a fiberoptic bronchoscope (FOB) and/or differential auscultation of the two lungs.

More recently, there has been increased use of ultrasonography at the bedside in various clinical locations including the Pediatric ICU and the operating room. Ultrasonography is painless, non-invasive and carries no risk. Given its ease of use and non-invasive nature, ultrasound is being used more frequently to make thoracic diagnoses including hemothorax, pneumothorax, pneumonia, and ARDS.³⁻⁸ More recently, preliminary data from three studies in adults suggest that ultrasound can be used to confirm lung isolation during SLV.⁹⁻¹¹ When the lung is not ventilated, there is no pleural movement noted (absence of lung sliding and no B-lines) and as the lung is non-mobile, the cardiac impulses may be transmitted through the lung to the chest wall and can be seen (presence of lung pulse). To date, there is only one anecdotal report of the intraoperative use of thoracic ultrasonography in the pediatric-aged patient.¹² The purpose of the current study is to prospectively evaluate the usefulness of thoracic ultrasonography in demonstrating effective lung isolation during SLV in the pediatric patient. Our primary hypothesis is that ultrasound will accurately verify lung separation during SLV, as compared to FOB.

- 3.2 This would provide a rapid and non-invasive means to demonstrate effective lung isolation without the time, cost, and invasive nature of direct visualization using a FOB.

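### The 80% accuracy hypothesis in 2.2 has no planned analysis, and the power figure in 12.2 is for a one-sample test that 17.1 does not run

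*Combined protocol and SAP*

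**What the plan says.** All references are to the combined protocol and SAP.

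- **2.1** sets an estimation aim: "to determine the accuracy of auscultation and ultrasonography for confirming lung isolation during SLV", with FOB as the gold standard.
- **2.2** hypothesises that "ultrasonography will have at least 80% accuracy for verifying lung separation during SLV as confirmed by FOB; and will have greater accuracy than auscultation".
- **3.1** words the primary hypothesis without any threshold: "Our primary hypothesis is that ultrasound will accurately verify lung separation during SLV, as compared to FOB".
- **12.2** takes 85% as the overall accuracy of ultrasound, citing a previous study that reported 84% to 89%. It then says that a two-tailed "one-sample test of proportions would have >80% power to detect a difference of at least 10% when 80 patients are enrolled". It does not say whether 85% is the null or the true value, in which direction the 10% runs, or what alpha is.
- **17.1** compares accuracy, sensitivity and specificity between ultrasound and auscultation, "using FOB confirmation of one-lung isolation as the reference standard) using paired tests of proportions". Apart from the comparison of procedure times, that is the whole analysis plan.

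**The concern.** The hypothesis has two parts and the analysis plan serves one. A paired test can show that ultrasound beats auscultation. It says nothing about whether ultrasound reaches 80%. No interval, one-sample test or decision rule refers to that figure.

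The plan also leaves open what reaching 80% means. Given 2.1 and 3.1, the benchmark in 2.2 could be a formal hypothesis or an expectation about the observed proportion. If the reading is not fixed in advance, it may be chosen once the data are known.

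The sample size argument has a matching gap. Its one power figure is for a test that will not be run, and the test that will be run has no power figure. A reader could take the figure in 12.2 as support for either half of 2.2. It supports neither.

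**Working it through.** **Inputs.** From the documents: n = 80, accuracy 85% (source range 84% to 89%), difference 10%, two-tailed (12.2); benchmark 80% (2.2). Assumed: alpha 0.05 and one verdict per patient. Auscultation accuracy and discordance are not in the documents and are varied below.

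**Step 1: the plan's own figure.** For null p0 and true p1, the normal approximation is

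power = Φ( [ |p1 − p0| − 1.96·√(p0(1−p0)/80) ] / √(p1(1−p1)/80) ).

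With p0 = 0.85 and p1 = 0.95: (0.10 − 1.96 × 0.0399)/0.0244 = 0.89, so power is 81.4%. The last row puts the 80% benchmark into the same formula: (0.05 − 1.96 × 0.0447)/0.0399 = −0.94.

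| Null | True | Normal | Exact binomial |
|---|---|---|---|
| 85% | 95% | 81.4% | 78.9% |
| 95% | 85% | 90.5% | 86.6% |
| 75% | 85% | 55.1% | 57.6% |
| 85% | 75% | 67.3% | 54.3% (equal-tailed) to 64.4% (minimum-likelihood) |
| **80%** | **85%** | **17.3%** | **13.5%** |

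The stated figure is reproduced only when 85% is set against 95%, and with 85% as the null the exact test falls just short. Neither of those pairings tests a hypothesis in 2.2. If 85% is the true accuracy and the null lies 10 points below it, power is 55% to 58%.

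**Step 2: possible readings of the 80% benchmark.** Let X be the number correct, binomial(80, p). The Clopper-Pearson two-sided 95% lower limit is 79.7% at 71/80 and 81.2% at 72/80. The one-sided 95% lower limit is 79.7% at 70/80 and 81.2% at 71/80.

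| Reading | Needs | True 80% | True 85% | True 89% |
|---|---|---|---|---|
| Point estimate at least 80% | 64/80 | 57% | 92% | 99% |
| One-sided 95% lower limit above 80% | 71/80 | 2.9% | 22% | 62% |
| Two-sided 95% lower limit above 80% | 72/80 | 1.3% | 13% | 48% |

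**Step 3: how often the reading decides the answer.** The point estimate and the two-sided limit disagree when X is 64 to 71. At true 85%, P(X ≥ 64) − P(X ≥ 72) = 0.916 − 0.134 = 0.782. The same probability is 78% at 84%, 52% at 89% and 55% at 80%. With the one-sided limit the disputed range is 64 to 70, and its probability at 85% is 0.916 − 0.221 = 0.695.

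**Step 4: the paired test in 17.1.** Exact McNemar power is summed over the binomial number of discordant pairs, with ultrasound at 85%. Discordance (in brackets) is smallest when no pair has auscultation alone correct.

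| Auscultation | Maximum discordance | Independent errors | Minimum discordance |
|---|---|---|---|
| 60% | 84% (0.55) | 93% (0.43) | >99% (0.25) |
| 65% | 68% (0.50) | 79% (0.395) | >99% (0.20) |
| 70% | 45% (0.45) | 54% (0.36) | 99% (0.15) |
| 75% | 23% (0.40) | 27% (0.325) | 82% (0.10) |
| 80% | 8% (0.35) | 9% (0.29) | 21% (0.05) |

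The paired test may be well or poorly powered; the documents do not allow one to say which.

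**Step 5: precision at n = 80.** An observed 68/80 (85%) has an exact 95% CI of 75.3% to 92.0%.

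**The case against.** The strongest reply is that 80% is only an expectation. 2.1 is an estimation aim, 3.1 gives no threshold, and 17.1 cannot compare accuracies without estimating them, so there will be a figure to set beside 80%. No formal success claim at 80% appears anywhere. That is a fair reading, but 2.2 presents the benchmark as the study's hypothesis, and the plan must say which it is. Even on the descriptive reading no interval is planned.

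The power figure can also be defended: it reproduces under a standard formula with the usual alpha. That stands. The fault is that it is attached to no planned analysis, not that the arithmetic is impossible.

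The calculations assume one verdict per patient, whereas 4.1 mentions both lung fields. With 160 independent verdicts, an optimistic assumption, all four 10-point pairings in step 1 would exceed 80% power (75% against 85% gives 88%). However, 12.2 counts patients, and power against 80% would still be only 30% to 34%.

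The 78% uses the stricter limit; with the one-sided limit it is 70%, and both fall if true accuracy is 89%. Finally, the paired-power figures show missing information, not inadequate power. Both points stand, and neither removes the mismatch between 12.2 and 17.1.

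**Conclusion.** The concern holds and should be settled before analysis. Half of the hypothesis in 2.2 has no planned analysis, and nothing in 17.1 corresponds to the test that justifies n = 80.

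At the plan's own 85%, the point-estimate and two-sided lower-limit readings would give opposite answers on the 80% benchmark in about 78% of such studies. A formal two-sided test against 80% would have 13% to 17% power. These figures rest on two-sided alpha 0.05 and one verdict per patient. No claim is made that the paired comparison is underpowered.

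**What to change.** **In 17.1:**

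- Add that ultrasound accuracy will be reported with an exact 95% CI.
- State before analysis how the 80% benchmark will be judged. A lower limit above 80% is one suitable rule: 72/80 with a two-sided 95% limit, 71/80 with a one-sided 95% limit.
- If no formal rule is wanted, present 80% as an expectation and report the estimate with its CI, without claiming that the benchmark has been shown. A bare 64/80 rule is weak evidence, since it is met 57% of the time when true accuracy is exactly 80%.
- Keep the paired comparison, name the test, and report the paired difference with its 95% CI.
- As a minor clarification, say that the patient is the unit of analysis.

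**In 12.2:** replace the single power figure with figures for the planned analyses: expected precision, the power of any 80% rule adopted, and paired-test power over stated auscultation accuracies and discordance.

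**Cost:** a few lines and no extra patients. The drawback is that stated power for the 80% hypothesis becomes much less favourable (13% to 22% at 85% under a lower-limit rule), so n = 80 would rest on precision and the paired comparison. Reaching 80% power for the two-sided rule at 85% would take roughly 470 to 495 patients (471 by the normal formula; the exact test stays above 80% from 494). That is not proposed.
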